3.2.2 Secondary objectives and endpoints

Secondary objective 1

- To evaluate the effect of early ART initiation, with or without having received VRC01 in the immediate pre-HIV acquisition period and/or during early infection on the development of anti-HIV immune responses and on the potential association of those immune responses with time to meeting criteria for ART re-initiation in participants undergoing ATI

Secondary endpoints 1

- Response rate, magnitude, and polyfunctionality of HIV-specific CD4+ and CD8+ T-cell responses as measured by flow cytometry
- Magnitude and breadth of neutralizing antibody (nAb) responses against autologous and heterologous HIV isolates, as measured by TZM-bl neutralization assay
- Non-neutralizing, Fc γ R-mediated antibody effector functions such as antibody-dependent cellular cytotoxicity (ADCC), antibody-dependent cellular phagocytosis (ADCP), and virion capture
- Frequency of dendritic cell activation and maturation markers, as measured by flow cytometry or other cell phenotyping assays
- Frequency of T- and B-cell activation and exhaustion markers, as measured by flow cytometry or other cell phenotyping assays

Secondary objective 2

- To evaluate the effect of early ART initiation, with or without having received VRC01 in the immediate pre-HIV acquisition period and/or during early infection on viral load in participants undergoing ATI

Secondary endpoint 2

- Cumulative incidence of participants with viral load ≥ 200 at weeks 8, 16, and 24

Secondary objective 3

- To evaluate the effect of early ART initiation, with or without having received VRC01 in the immediate pre-HIV acquisition period and/or during early infection on HIV reservoir size before and after ATI, and whether HIV reservoir measurements are associated with time to meeting criteria for ART re-initiation in participants undergoing ATI

Secondary endpoint 3

- Frequency of CD4+ T cells carrying intact and/or total pro-viral HIV DNA, replication competent virus, and/or cell-associated HIV RNA

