1.1 Précis

While plasma viremia rebounds rapidly in most chronically HIV-infected individuals upon cessation of therapy, early initiation of ART after HIV diagnosis has been associated with later ART-free virologic control in individuals known as “post-treatment controllers” (PTCs). Similarly, preclinical (eg, murine, nonhuman primate [NHP]) and clinical evidence suggest that the presence of broadly neutralizing anti-HIV-1 antibodies (bnAbs), even at a concentration, or with a neutralization sensitivity profile, insufficient to prevent HIV acquisition, may nevertheless modulate the autologous response to HIV infection in ways that help set the stage for later durable virologic control. There is also evidence suggesting that early ART initiation and the presence of bnAbs at the time of or soon after HIV infection may be capable of limiting the establishment of and decreasing the size of viral reservoirs. Whether and how these effects might act together to support durable viral control, and what biomarkers may predict such control, is unknown.

The Antibody Mediated Prevention (AMP) studies HVTN 704/HPTN 085 and HVTN 703/HPTN 081, phase 2b studies assessing the ability of the CD4 binding site bnAb VRC01 to prevent HIV-1 infection, provide a unique opportunity to assess the impact of these hypothesized effects. The AMP studies currently have the only cohort of HIV-1–infected individuals who were diagnosed soon after acquisition, who initiated ART relatively soon after diagnosis, and a subset of whom had bnAb present at or near the time of infection. A pause in antiretroviral treatment—that is, an ATI—is the only way to determine whether early ART initiation with and without VRC01 circulating around the time of HIV acquisition, results in blunted, delayed, or absent viral rebound following discontinuation of ART, or subsequent immune control of any rebound that may be observed. If such an impact is observed, ATI is also the best means of assessing mechanisms and identifying predictive biomarkers of that impact through assessment of innate, cellular, and humoral markers along with characterization of the viral reservoir. Extensive virologic, immunologic, and safety monitoring will be conducted, and the trial has been formulated for consistency with recent consensus guidelines on the design and conduct of ATI studies (2, 3), particularly with respect to risk mitigation.

The study schema is shown below.

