1.2 Schema

	SCREEN	PRE-DISCONTINUE ART	SCHEDULE 1			SCHEDULE 2			PRE-REINITIATE ART	SCHEDULE 3		
			ATI WEEKS 0-8	ATI WEEKS 10-24	ATI WEEKS 28-52 ¹	ATI + Viremia WEEKS 0-8	ATI + Viremia WEEKS 10-36	ATI + Viremia WEEKS 40-52 ²		FOLLOW UP ON ART WEEKS 0-12	FOLLOW UP ON ART WEEKS 12-28	FOLLOW UP ON ART WEEKS 40-52
Plasma HIV RNA	✓	✓	WEEKLY	Q2 WEEKS	Q4 WEEKS	WEEKLY	Q2 WEEKS ³	Q4 WEEKS	✓	Q2 WEEKS	Q4 WEEKS	Q12 WEEKS
CD4+ & CD8+ T cell counts	✓	✓	Q2 WEEKS	Q4 WEEKS	Q8 WEEKS	Q2 WEEKS	Q4 WEEKS ⁴	Q8 WEEKS	✓	Q4 WEEKS	Q8 WEEKS	Q12 WEEKS
Hematology & Chemistries	✓	✓	Q4 WEEKS		Q8 WEEKS	Q4 WEEKS		Q8 WEEKS	—	Q4 WEEKS	Q12 WEEKS	Q12 WEEKS

¹ QUARTERLY FOLLOW-UP VISITS MAY CONTINUE BEYOND WEEK 52 FOR PARTICIPANTS WHO DO NOT MEET CRITERIA FOR TRANSITION TO SCHEDULE 2.

² QUARTERLY FOLLOW-UP VISITS MAY CONTINUE BEYOND WEEK 52 FOR PARTICIPANTS WHO DO NOT MEET CRITERIA FOR ART RE-INITIATION.

³ OR WEEKLY FOR WEEKS 10-24, IF VL ≥ 200 copies/mL

⁴ OR Q2 WEEKS FOR WEEKS 10-24 IF VL ≥ 200 copies/mL

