Bar et al (48) reported on 24 chronically infected participants in 2 cohorts; in one cohort (A5340), participants had been taking ART for 3.8-6.0 years (median 4.7) and in the other (15-I-0140) participants had been taking ART for 7.7-13.3 years (median 10.0). All participants received VRC01, followed by an ATI, which ended upon confirmation of viral rebound. Median time to viral rebound was 4 weeks in the A5340 trial and 5.6 weeks in the 15-I-0140 trial. VRC01 slightly delayed plasma viral rebound compared with historical controls but did not sustain viral suppression. No safety issues were observed in either cohort.

Clarridge et al (94) reported on the 10 chronically infected participants in the 15-I-0140 cohort who received VRC01 immediately before and during ATI (median of 8 weeks, range 3-17 weeks). The length of the treatment interruption was governed by the time to meeting ART re-initiation criteria, which included a decrease of > 30% from the baseline CD4+ T-cell count or an absolute CD4+ T-cell count < 350 cells/mL, sustained (≥ 4 weeks) plasma viremia > 1,000 copies/mL, any HIV-related symptoms, or pregnancy (48, 94). During treatment interruption, total HIV DNA in CD4+ T cells increased significantly from pre-interruption levels and all participants rebounded, with median peak viremia of 30,950 copies/mL observed (range 340 - 273,221). By 6-12 months post-ATI, reservoir size, including the proportion of near full-length, genome-intact proviral sequences and structurally defective proviral sequences, and immune markers of exhaustion and activation returned to pre-ATI levels; CD4+, CD8+ (including activated CD8+), B, and NK cell levels also returned to pre-ATI levels; and there

was no evidence of emergence of antiretroviral drug resistance mutations in intact proviral DNA sequences.

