3.2.3 Exploratory objectives

Exploratory objective 1

- To assess participant and potential participant motivations, perceptions and tolerance for ATIs, for prolonged viremia, and for trial requirements (eg, ART switches, barrier protection for all sexual activity)

Exploratory objective 2

- To assess social benefits (eg, altruism) and negative social impacts, including but not limited to anxiety regarding being off ART and becoming viremic again and fear of inadvertent HIV transmission to partners

Exploratory objective 3

- To assess participant and potential participant decision-making quality, including perception of being informed, clarity and support in decision making and satisfaction with their choice regarding participation

Exploratory objective 4

- To evaluate the effect of VRC01 received in the immediate pre-HIV acquisition period and/or during early infection on viral kinetics in participants undergoing ATI

Exploratory objective 5

- To determine whether characteristics of the transmitted/founder (T/F) viruses, rebound virus(es), and/or baseline viral reservoirs, including relative VRC01 sensitivity or resistance, are associated with virologic control or the development of anti-HIV immunity among individuals who acquired HIV during their participation in HVTN 703/HPTN 081

Exploratory objective 6

- To assess whether host genetics (eg, HLA type, CCR5 heterozygosity) and sex assigned at birth are associated with time to meeting ART re-initiation criteria among VRC01 or placebo recipients who acquired HIV during their participation in HVTN 703/HPTN 081

Exploratory objective 7

- To qualitatively characterize the immune responses and reservoir characteristics of controllers and non-controllers in this cohort and to compare these to immune responses and reservoir characteristics of historical cohorts (ie, SPARTAC African and non-African cohorts, described in Gossez et al (1), comprising individuals who initiated ART early in HIV infection without other interventions)

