4.2.4 Secondary analyses of immune responses, reservoir measurements and viral load

Analyses of immune responses and reservoir measurements will be descriptive using appropriate plotting techniques for describing measurements at a fixed time point (eg, boxplots and barplots) or longitudinally (eg, spaghetti plots) separately by treatment group. In addition, if enough samples are assayed we plan to do inferential and descriptive analyses as described in the following sections.

4.2.4.1 Evaluate the difference in anti-HIV immune responses or reservoir size between VRC01 and placebo recipients

TMLE will be used to estimate mean endpoints in each of the infected VRC01 and infected placebo groups, as well as the mean difference, all with 95% confidence intervals and associated 2-sided p-values, where the TMLE controls for all baseline covariates thought to potentially predict both HIV-1 infection and one of the secondary endpoints under study. This is needed for controlling for potential postrandomization selection bias given that analyzed treatment groups are selected postrandomization.

4.2.4.2 Assess whether anti-HIV immune responses or reservoir size are associated with time to meeting ART re-initiation criteria

Cox regression will be used to estimate cumulative incidence over time for groups defined by levels of immune response or reservoir size for each treatment group.

4.2.4.3 Time to viral load > 200

Secondary endpoint 2 is time until the participant has a viral load > 200. The same methodology used to assess time to ART re-initiation criteria will be used for this endpoint. In this analysis we will compare cumulative incidence at week 8 in each of the infected VRC01 and infected placebo groups supplemented by a sensitivity analysis based on cumulative incidence at weeks 8, 16, and 24.

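### Secondary objective 2, the effect on viral load, has no quantitative endpoint; its single 200 copies/mL threshold is insensitive to a rebound that is lower but not delayed

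*Protocol*

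**What the plan says.** Protocol section 3.2.2 gives secondary objective 2, on viral load during ATI, a single endpoint: "Cumulative incidence of participants with viral load ≥ 200 at weeks 8, 16, and 24". SAP section 4 repeats it. Protocol section 4.2.4.3 restates it for analysis: "Secondary endpoint 2 is time until the participant has a viral load > 200". The method is the one used for time to the ART re-initiation criteria. The main comparison is early: "In this analysis we will compare cumulative incidence at week 8 in each of the infected VRC01 and infected placebo groups", with weeks 8, 16 and 24 as a sensitivity analysis. SAP section 6.4 says the same.

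The précis (protocol section 1.1) asks whether early ART, with or without VRC01, "results in blunted, delayed, or absent viral rebound following discontinuation of ART, or subsequent immune control of any rebound that may be observed".

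Quantitative viral load has two other places in the plan. Exploratory objective 4 (protocol section 3.2.3) reads "To evaluate the effect of VRC01 received in the immediate pre-HIV acquisition period and/or during early infection on viral kinetics in participants undergoing ATI"; no endpoint or method follows. SAP section 10.2 lists participant-level longitudinal plots, one of them restricted to participants who entered Schedule 2.

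Under the schema (protocol section 1.2), viral load is drawn weekly in weeks 0–8 of Schedules 1 and 2. It is then drawn every two weeks, later every four, with a provision in Schedule 2: "OR WEEKLY FOR WEEKS 10-24, IF VL ≥ 200 copies/mL".

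**The concern.** Once a participant has crossed 200 copies/mL, a viral load of 500 and one of 200,000 count the same. Absent or delayed rebound moves this endpoint. A rebound that arrives on time but is lower barely does.

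The protocol's own background suggests that this matters:

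- In the macaque study that the protocol hopes to translate to humans, five of the six controllers suppressed virus only after an initial rebound (sections 2.3.2 and 2.8).
- Three of the five African SPARTAC controllers had transient viremia of 560–1,690 copies/mL (section 2.2.2). Such an episode by week 24 would count as an event here.
- In the ACTG meta-analysis, only 9% of acute-treated and 15% of early-treated participants were still suppressed at 12 weeks (section 2.2.1). By week 16 a threshold endpoint may have little room to move.

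At stake is a secondary conclusion of no effect on viral load when the level of viremia did differ, in a study of 16 to 61 people.

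**Working it through.** **1. The plan's own power figures.** No power is given for secondary endpoint 2. For the primary endpoint (protocol section 4.1.1), the Weibull median is exp(2.932) × (ln 2)^(1/2.014) = 18.77 × 0.834 = 15.6 weeks, as stated. A 60% hazard reduction multiplies the median by 0.4^(−1/2.014) = 1.58, the stated 58% increase. A 10,000-trial log-rank simulation with 20% annual exponential censoring and a 72-week cap gives 71.7% (stated 72%) for 13 placebo and 27 VRC01 recipients, and 63.3% (stated 62%) for 18 and 14. All 24 cells of protocol Table 4-1 reproduce within 2 points.

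**2. Spread of rebound height.** The only figure in the documents is in protocol section 2.4: ten chronically infected participants given VRC01 around ATI, with median peak 30,950 copies/mL and range 340 to 273,221.

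- log10 median = 4.491
- log10 range = 5.437 − 2.531 = 2.905
- The expected range of ten normal values is 3.078 SD, so SD = 2.905 / 3.078 = 0.944

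**3. How far each threshold moves under a tenfold lower peak** (log10 mean 4.491 against 3.491, normal log10 peaks):

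| Peak reaches | Control | Tenfold lower |
|---|---|---|
| 200 (log10 = 2.301) | Φ[(4.491 − 2.301)/0.944] = Φ(2.32) = 99.0% | Φ[(3.491 − 2.301)/0.944] = Φ(1.26) = 89.6% |
| 1,000 (log10 = 3) | Φ(1.58) = 94.3% | Φ(0.52) = 69.8% |

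A tenfold effect moves the 200-copy endpoint by about 9 points. It moves the 1,000-copy level, which is part of the re-initiation criterion, by about 25 points.

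**4. Power for that effect.** Rebound onset is the same in both arms (Weibull shape 1.5, median 3, 5 or 8 weeks; assumed), and crossing 200 is read on the Schedule 1 visit grid to week 24. Group sizes are 13/27 and 18/14, with two-sided alpha 0.05.

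| Analysis, 1.0 log10 lower peak, SD 0.94 | Power |
|---|---|
| Log-rank, time to VL ≥200 | 10–12% |
| z test, week 8 cumulative incidence | 4–14% |
| Log-rank, simplified re-initiation event (peak ≥1,000, 5-week lag) | 24–38% |
| t test on log10 peak | 86% (13/27), 82% (18/14) |
| Rank test on 4-week average log10 VL after first VL ≥200, growth 0.5–1.5 log10 per week | about 53–83% |

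The four-week average has less power than the peak because the window includes the rise. It is the relevant figure, since it is the measure proposed below.

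**5. Sensitivity.** For SD 0.7–1.2, the 200-copy log-rank gives 6–16%. Over the same SDs, a rank test using peak in place of the average, with onset median 5 weeks and participants who never reach 200 ranked lowest, gives 59–98%. For a 0.5 log10 effect, the 200-copy log-rank gives 5–8%, against 22–56% for log10 peak.

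**6. Does virologic re-initiation cut into a four-week window?** Through Schedule 2 week 24, the virologic criterion needs at least 4 consecutive weeks at ≥1,000 copies/mL (protocol section 3.3.3). The first value ≥1,000 cannot precede the first value ≥200, so this criterion cannot be met before the window has run. The separate ≥200 criterion applies only after Schedule 2 week 24.

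**The case against.** A reader might infer that a blunted rebound would be nearly undetectable in this trial, or that control after rebound goes unmeasured. The documents do not support either reading.

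- Primary endpoint 1 includes sustained control, defined as at least 24 weeks off ART without meeting the re-initiation criteria (protocol section 3.2.1). A participant who rebounds and then controls can count as a success.
- The virologic criterion combines ≥1,000 copies/mL for at least 4 weeks with a 0.5 log rule (section 3.3.3), so the primary endpoint responds to height in part.
- Viral kinetics is an exploratory objective, individual trajectories are plotted, and all the viral loads are kept.

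This limits the point to one secondary objective. It does not remove it, because none of these supplies a prespecified quantitative comparison of the arms.

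Three further objections have weight. The SAP describes itself as covering safety reports, so its silence on kinetics is weak evidence of omission; but the protocol gives no method either. The effect size and equal onset are assumptions that favour a quantitative measure: if blunting also slows growth, crossing 200 is delayed and the existing endpoint gains power. The SD comes from chronically infected people, whereas this cohort was treated early.

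Finally, the study is exploratory, and one can argue that the natural home for such a measure is exploratory objective 4. That is a defensible placement, provided that an endpoint and a method are written down.

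**Conclusion.** The point holds for secondary objective 2. An objective on viral load is served only by a 200-copy threshold, and the plan nowhere specifies a quantitative viral load comparison of VRC01 with placebo. For a tenfold lower, undelayed rebound, the 200-copy analyses have about 4–15% power, against roughly 53–83% for a four-week average log10 viral load compared by ranks. These figures rest on a log10 SD of about 0.94 taken from the range in ten chronically infected participants, normal log10 peaks, equal onset in both arms, and growth of 0.5–1.5 log10 per week. The direction is firmer than the exact values: the threshold discards height by construction. The primary analysis is unaffected, and this is an inexpensive improvement to a secondary objective.

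**What to change.** Keep the 200-copy endpoint. Add a quantitative one to secondary endpoint 2 (protocol sections 3.2.2 and 4.2.4.3; SAP sections 4 and 6.4), or at minimum make it the stated endpoint of exploratory objective 4:

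- **Measure:** time-averaged log10 HIV RNA over the first 4 weeks after the first VL ≥200, with values below the LLOQ set to one fixed value.
- **No rebound:** participants followed off ART with no VL ≥200 by week 24 take the lowest rank, so that everyone so followed stays in the comparison.
- **Incomplete data:** for non-virologic ART re-initiation inside the window, use the off-ART values available. State a separate rule for participants who leave or restart ART before week 24 without a VL ≥200, since they are not known controllers.
- **Test:** Wilcoxon, VRC01 against placebo, supported by a covariate-adjusted rank or proportional-odds model.
- **Interpretation:** the same caveat on selection by infection after randomization that protocol section 4.2.3 attaches to the other arm comparisons.

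A four-week window describes early height; later control remains with the primary endpoint.

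In the same edit, reconcile ≥200 in the endpoint definition with >200 in the analysis section, and the three listed weeks with the analysis that puts week 8 first.

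The cost is wording in both documents, with no new blood draws. The drawback is one more secondary comparison; the plan already makes no multiplicity adjustment across secondary endpoints (protocol section 4.2).

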3.2.3 Exploratory objectives

Exploratory objective 1

- To assess participant and potential participant motivations, perceptions and tolerance for ATIs, for prolonged viremia, and for trial requirements (eg, ART switches, barrier protection for all sexual activity)

Exploratory objective 2

- To assess social benefits (eg, altruism) and negative social impacts, including but not limited to anxiety regarding being off ART and becoming viremic again and fear of inadvertent HIV transmission to partners

Exploratory objective 3

- To assess participant and potential participant decision-making quality, including perception of being informed, clarity and support in decision making and satisfaction with their choice regarding participation

Exploratory objective 4

- To evaluate the effect of VRC01 received in the immediate pre-HIV acquisition period and/or during early infection on viral kinetics in participants undergoing ATI

Exploratory objective 5

- To determine whether characteristics of the transmitted/founder (T/F) viruses, rebound virus(es), and/or baseline viral reservoirs, including relative VRC01 sensitivity or resistance, are associated with virologic control or the development of anti-HIV immunity among individuals who acquired HIV during their participation in HVTN 703/HPTN 081

Exploratory objective 6

- To assess whether host genetics (eg, HLA type, CCR5 heterozygosity) and sex assigned at birth are associated with time to meeting ART re-initiation criteria among VRC01 or placebo recipients who acquired HIV during their participation in HVTN 703/HPTN 081

Exploratory objective 7

- To qualitatively characterize the immune responses and reservoir characteristics of controllers and non-controllers in this cohort and to compare these to immune responses and reservoir characteristics of historical cohorts (ie, SPARTAC African and non-African cohorts, described in Gossez et al (1), comprising individuals who initiated ART early in HIV infection without other interventions)

3.3 ATI

For all participants, ATI begins with cessation of ART in Schedule 1, *Monitoring ATI*. Participants on ATI (ie, Schedule 1 or 2) who do not meet criteria for moving to the next visit schedule (ie, viral rebound or re-initiating ART) should continue on their current ATI visit schedule, including extended visits (as appropriate) until such time as they move to the next visit schedule or are terminated from the study. Schedule 1 and Schedule 2 extended visits occur quarterly and are designated as Visits Type A and Type B, with procedures specified for each visit type, in the laboratory and clinical procedures tables (see [Appendix E](#), [Appendix F](#), [Appendix H](#), [Appendix I](#), and [Appendix K](#)). For participants who meet criteria for reinitiating ART but decline to do so, see [Section 3.3.4](#).

3.3.1 Transition from Schedule 1, *Monitoring ATI* to Schedule 2, *ATI monitoring with viremia*

For participants on Schedule 1, *Monitoring ATI*, the following virologic criterion will trigger a transition to Schedule 2, *ATI monitoring with viremia*:

- Confirmed VL ≥ 200 copies/mL (ie, on 2 consecutive samples).

A confirmatory sample should be drawn at the next visit (within approximately 1-2 weeks) following the first VL result ≥ 200 copies/mL (see HVTN 805/HPTN 093 SSP for details).

